12.4 PARTICIPANT AND DATA CONFIDENTIALITY19

CONFIDENTIAL

This material is the property of the NYU School of Medicine and Langone Medical Center. Do not disclose or use except as authorized in writing by the study sponsor

13	DATA HANDLING AND RECORD KEEPING	19
13.1	DATA COLLECTION AND MANAGEMENT RESPONSIBILITIES	19
13.2	STUDY RECORDS RETENTION.....	19
13.3	PROTOCOL DEVIATIONS	19
13.4	PUBLICATION AND DATA SHARING POLICY	20
14	STUDY FINANCES.....	20
14.1	COSTS TO THE PARTICIPANT	20
14.2	PARTICIPANT REIMBURSEMENTS OR PAYMENTS.....	20
15	CONFLICT OF INTEREST POLICY.....	20
16	ATTACHMENTS	21

CONFIDENTIAL

List of Abbreviations

AE	Adverse Event/Adverse Experience
HIPAA	Health Insurance Portability and Accountability Act
ICF	Informed Consent Form
IRB	Institutional Review Board
PI	Principal Investigator
VR	Virtual Reality
PwMS	People with Multiple Sclerosis

CONFIDENTIAL

Protocol Summary

[figure not shown]
Title	Virtual Reality (VR) to improve Quality of Life in Patients diagnosed with Neurological Disorders
Short Title	VR to improve Quality of Life
Brief Summary	Participants with neurological disorders will be recruited to complete sessions of virtual reality (VR) immersion. VR has been shown to have therapeutic benefit in certain patient populations and requires further clinical study to determine the extent to which VR can be used to rehabilitate and reduce symptom burden. This study seeks to pilot newly developed VR methods and collect preliminary data in order to support research grants and inform larger clinical trials. This proposed study will explore the tolerability and preliminary efficacy of Virtual Reality (VR), specifically to determine whether VR can acutely reduce the severity of symptom burden caused by neurological disorders. Additionally, a second group of MS participants with clinically significant pain will be recruited to test the analgesic effects of VR.
Phase	N/A
Objectives	Specific Aim 1: To test the feasibility and tolerability of immersive VR therapy in patients with neurological disorders. Specific Aim 2: To measure the efficacy of a VR program to manage chronic pain for people with multiple sclerosis.
Methodology	Study Group 1: Open-Label Study Group 2: Single blinded, randomized treatment allocation to one of two VR treatment conditions
Endpoint	Completion of up to twelve one-hour sessions of VR alongside study measures taken at the end of the last completed session
Study Duration	Participants may complete sessions for up to one year following consent.
Participant Duration	Study group 1: Approximately 12 hours over 12 days. Study group 2: Approximately 10 hours over 9 days.
Duration of IP administration	Up to 12 1-hour sessions, totaling twelve hours.
Population	Study group 1: Patients at least 12 years of age with a confirmed diagnosis of a neurological disorder Study group 2: Patients between the ages of 18 and 79 with a confirmed MS diagnosis and symptoms of MS pain.
Study Sites	NYU Ambulatory Care Center
Number of participants	104
Description of Study Agent/Procedure	HTC Vive VR Headset with interactive and/or relaxing games/video. The VR system and accompanying content will be configured by study personnel for comfort and therapeutic benefit.
Reference Therapy	N/A
Key Procedures	N/A
Statistical Analysis	Analysis will focus on change in quality of life measures from baseline to follow-up as well as the number of successfully completed VR sessions.

CONFIDENTIAL

[figure not shown]
This material is the property of the NYU School of Medicine and Langone Medical Center. Do not disclose or use except as authorized in writing by the study sponsor

Schematic of Study Design

Study Group 1 (Neurological Disorders):

Study Group 2 (Chronic Pain in MS):

CONFIDENTIAL

This material is the property of the NYU School of Medicine and Langone Medical Center. Do not disclose or use except as authorized in writing by the study sponsor

1 Key Roles

Principal Investigator:

[name], Director of Research
New York University Langone Health - Multiple Sclerosis Comprehensive Care Center
[name]
[contact]
[contact]

Co-Investigator:

[name].
New York University Langone Health - Multiple Sclerosis Comprehensive Care Center
[name]
[contact]
[contact]

2 Introduction, Background Information and Scientific Rationale

2.1 Background Information and Relevant Literature

VR has become increasingly integrated into modern medicine, with both medical students and patients receiving education and receiving experimental rehabilitation therapies through the use of the VR medium [1]. Patients with neurological disorders stand to benefit from VR therapies [2, 3], as these diseases are often chronic and limited in treatment options.

In a series of preliminary studies, Hoffman et al (2004) investigated VR and subjective pain ratings with use of painful thermal stimuli and fMRI to monitor pain-related neural activity. VR reduced pain-related activity in all five regions of focus (Anterior Cingulate Cortex, Primary and Secondary Somatosensory Cortex, Insula, and Thalamus)[4]. In addition, VR reduced subjective pain-related reports as well as reduction in brain activity, displaying subjective and objective correlation of emotional and sensory aspects of pain experience [4]. In a separate study by Hoffman et al (2001), burn victims reported a lower subjective pain rating when experiencing VR while undergoing wound care than those who did not experience distraction. It was found that the magnitude of pain reduction did not diminish with repeated use[5]. The study results imply that VR use may have potential for implementation in other populations that experience neuropathic pain.

VR immersion therapy presents itself as a noninvasive, riskless, rehabilitative treatment with an abundance of promise for patients with unmet treatment needs [6]. VR immersion has been utilized for exposure therapy in posttraumatic stress disorders (PTSD) in Vietnam veterans as described in a case study by Rothbaum et al (1999)[7]. The patient was immersed in virtual environments in order to target memories triggered by each scene while being spoken to by the therapist through VR headset. Results indicated habituation and showed improvements on all measures of PTSD. PTSD scores using IES assessment lowered significantly following treatment end with sustained benefit for up to 6 months. Additionally, VR did not seem to create an adverse effect on conditions of depression, anxiety, or drug/alcohol use [7].

VR therapy using emotion-processing theory has been used to target anxiety disorders and fear arousal. Exposure therapy is a common treatment used to combat anxiety disorders such as specific phobias. Therapists attempt to desensitize the patient by associating relaxation techniques while presenting the feared object or situation [8]. VR allows for a passageway into exposure therapy whilst avoiding the actual fearful stimuli to the patient. Moreover, a study by Navarro-Haro et al. showed that participants who used VR in a mindfulness setting experienced subjective symptom relief in negative emotional states as well as reduced anxiety, sadness, and anger [9].

CONFIDENTIAL

This material is the property of the NYU School of Medicine and Langone Medical Center. Do not disclose or use except as authorized in writing by the study sponsor

2.2 Rationale

Neurological diseases can confer varying symptoms in patients' lives that may cause physical, emotional, or psychological deficits. Common impairments include chronic pain, fatigue, depressed mood, and fine or gross motor issues, all of which have the potential to drastically affect a person's quality of life. Pain in neurological conditions is rarely disease-specific and patients can experience different types of pain within the same disorder[10]. Researchers and clinicians have begun to look to VR-based treatment modalities to reduce the severity of symptoms experienced such as neuropathic pain [3, 11], psychological distress[7, 12], and self-efficacy [13, 14].

We propose that immersive VR may be an effective means of reducing patients' symptoms through engagement of novel and immersive stimuli [15]. Such immersion is made possible through the use of groundbreaking computer graphics, surround-sound audio, and display screen headsets with high resolutions and body-tracking devices that allow video interaction with users in real-time [8].

2.3 Rationale for PwMS and Chronic Pain

Pain is the most common symptom associated with MS, affecting as many as 80% of all patients. As in other conditions, pain in MS is typically managed using medications including opioids and other centrally active drugs (e.g, antiepileptic medications such as gabapentin). However, pain medications are often not completely effective and can lead to dependence[16]. Pain medication can have many troubling side effects that can exacerbate other MS symptoms including fatigue and cognition. Therefore, there remains a significant unmet need for effective and tolerable pain management options [17, 18].

2.4 Potential Risks & Benefits

2.4.1 Known Potential Risks

Per HTC Vive manufacturer's specifications, study technicians will ensure the area around the patient is safe and with no obstructions. Immersive VR will be used under the supervision of the research assistant in charge of the session. Immersive VR may cause dizziness, nausea, or headache. **However, such adverse events are highly infrequent and we expect that the proposed treatment to be highly tolerated. This study poses minimal risk to participants.**

If discomfort is great enough that the participant wants to cease the session, the experiment will stop and symptoms should resolve after a brief rest.

This study poses no greater risk for children.

2.4.2 Known Potential Benefits

Participants may experience benefit from this study such as improvement in their mood or physical sensations. Immersive VR therapy may reduce symptom severity experienced by those with neurological disorders.

3 Objectives and Purpose

Specific Aim 1: To test the feasibility and tolerability of immersive VR therapy in patients with neurological disorders.

The primary outcome will be the number of successfully completed VR sessions across all participants. Secondary outcomes will be the subjective assessment of tolerability and engagement. Participants will rate enjoyment, engagement, and any potential side effects of the VR therapy.

Specific Aim 2: To test the effects of immersive VR on symptom burden in patients with neurological disorders.

The primary outcome will be the change in dimensions of symptom burden in participants with neurological disorders. Universal symptom inventory measures (Patient Reported Outcomes Measurement Information System or PROMIS) will be administered before and after each session. A paired t-test will be used to determine whether the cohort has experienced statistically significant change following VR.

The secondary outcomes will include disease specific inventories (i.e. MFIS) which will be administered before and after each session and their change after VR will be evaluated.

CONFIDENTIAL

This material is the property of the NYU School of Medicine and Langone Medical Center. Do not disclose or use except as authorized in writing by the study sponsor

4 Study Design and Endpoints

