4.1 Description of Study Design

Study Group 1 (Neurological Disorders):

The study is intended as a pilot trial for VR in neurological conditions. An open-label design will be implemented. Once participants are found eligible, they will complete one full session of VR using a headset preconfigured by study personnel. Participants will complete up to twelve sessions of VR therapy that may extend as long as an hour in length. Total number of study visits will be up to the study personnel's discretion. Study personnel will guide VR headset placement and program assignment (i.e., interactive or passive catalogues).

Study Group 2 (Chronic Pain in MS): The study will include an arm for people with MS (PwMS) and chronic pain. We will determine the efficacy of VR for the management of chronic pain in PwMS. Participants in this study group will receive eight treatment sessions over four weeks. Participants will be blinded to the VR treatment catalogue they receive.

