4.2 Study Endpoints

4.2.1 Study Group 1 (Neurological Disorders): Study Endpoints

Primary study endpoint will be completion of at least one VR session and change in baseline measures.

Secondary study endpoint will be lack of tolerance of VR protocols. If a participant is unable to complete two full VR sessions due to any possible side effect (i.e. Dizziness or nausea) the session and participant's participation in the study will be terminated (see Assessment of Safety below).

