Participant personal information may be kept in Ripple™, a secure web application designed for the storing and management of personally identifying information of research participants. Ripple was initially developed at the University of Michigan to provide a user-friendly, web-based secure interface where research teams can centralize the storage and management of research participants' personal information, including name, participant ID, demographics, and study workflow (e.g., appointments). Participant information managed with ripple is private and secure. This information is kept in fully encrypted format inside dedicated databases that are segregated from other Ripple accounts and thus only authorized study staff will have access to the study data. Likewise, Ripple infrastructure complies with the privacy and security guidelines of the Health Insurance Portability and Accountability Act (HIPAA), including 2048-bit data encryption in transit and at rest, automatic logoff, audit trail, daily backups in triplicate dedicated servers, firewall, custom access permission for lab members, zxcvbn password strength estimation, and enterprise administrative safeguards to prevent unauthorized staff from accessing participant information. Furthermore, Ripple is used only for storing personally identifiable information of participants and is not used to capture other research data (e.g., questionnaires, health records, etc.). This ensures that the personally identifiable information and research data are segregated. Ripple is already being used at NYU Langone Health.

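### The Aim 1 feasibility primary is a count of completed sessions with no denominator, although staff set how many sessions each Group 1 participant is asked to do, and Section 4.2.1 words feasibility differently

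*Combined protocol and SAP*

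**What the plan says.** Section 3, Specific Aim 1, sets the feasibility primary: "The primary outcome will be the number of successfully completed VR sessions across all participants". The Statistical Analysis row of the Protocol Summary repeats it; analysis is to cover change in quality of life "as well as the number of successfully completed VR sessions". Neither place gives a rate or a per-participant summary.

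The number of sessions in Study Group 1 is not fixed. Section 4.1 says: "Total number of study visits will be up to the study personnel's discretion". Section 5.5 says the same of the visits a participant is asked to make, caps them at twelve, and allows the first session to be made the last. The Participant Duration row of the Protocol Summary gives a nominal figure, "Study group 1: Approximately 12 hours over 12 days", but nothing makes it binding.

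Section 4.2.1 words the Group 1 primary differently: "Primary study endpoint will be completion of at least one VR session and change in baseline measures". It adds lack of tolerance as a secondary endpoint.

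Section 9 gives Group 1 paired t-tests on symptoms, with means and standard deviations. It plans no analysis of session completion. Section 5.6 sets Group 1 at 60 participants, and Section 5.4 says that the group's main purpose is to show feasibility.

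**The concern.** A feasibility figure should tell the designers of the next trial what share of a course of VR patients will complete. A bare count can do that only if everyone is asked for the same number of sessions. Here staff choose the number, and may settle it after the first session. A low count could mean that patients tolerated VR poorly or that staff asked for few sessions; a high count could mean only that staff asked for many. Dividing by the number of participants does not help, because the mean per participant depends on staff choice in the same way.

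The second difficulty is that Sections 3 and 4.2.1 do not name the same feasibility primary. At least one completed session can be read as a proportion of the 60 enrolled, but it stops at session one. A team following the protocol could report either figure as the primary, and neither shows adherence over a course of sessions.

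**Working it through.** The plan has no calculation to reproduce: Group 1 has no target completion rate, precision or power, and Section 9 calls the choice of 60 partly arbitrary. The check is therefore arithmetic on the endpoint.

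**Inputs from the protocol:** 60 participants (Section 5.6); minimum 1 and maximum 12 sessions each (Section 5.5). All other values below are assumptions for illustration.

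**1. Range of the count at perfect tolerability.** Count = participants × sessions asked.
- All asked for 1: 60 × 1 = 60.
- All asked for 12: 60 × 12 = 720.

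This twelve-fold range comes from staff choice alone. It is a limiting bound, not a forecast. If the phrase about all participants also covers Group 2 (44 participants with eight fixed sessions), add 44 × 8 = 352 to each end: 412 to 1,072.

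**2. One count, several completion rates.** Take 240 completed sessions, 4 per participant.
- 4 planned each: 240 / (60 × 4) = 100%.
- 8 planned each: 240 / (60 × 8) = 50%.
- 12 planned each, the Protocol Summary's nominal figure: 240 / (60 × 12) = 33%.

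The mean is 240 / 60 = 4.0 in all three cases. Section 4.2.1's component is 100% in all three, since everyone completed at least one session.

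**3. Does the choice of denominator matter?** Assume 8 sessions planned each, half the participants stopped by staff at 4, and 95% of offered sessions completed.
- Planned: 60 × 8 = 480.
- Offered: 30 × 8 + 30 × 4 = 360.
- Completed: 0.95 × 360 = 342.
- Completed/offered: 342 / 360 = 95%. Completed/planned: 342 / 480 = 71%.

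If staff stop a quarter instead: offered 45 × 8 + 15 × 4 = 420; completed 0.95 × 420 = 399; 399 / 420 = 95% and 399 / 480 = 83%.

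Completed/offered does not move however many participants staff stop, so it would hide stopping because a participant was struggling. Completed/planned falls with every staff stop, including stops unrelated to tolerance. Neither is sufficient alone.

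**4. Precision of a completion proportion.** Half-width = 1.96 × √[p(1 − p) / (n × m) × (1 + (m − 1)ρ)], with n = 60, m sessions planned each, p = 0.80 assumed, and within-participant correlation ρ = 0.3 assumed (range 0.1 to 0.5).
- m = 4: 1.96 × √[0.16 / 240 × 1.9] = 7.0 points (5.8 to 8.0). Ignoring clustering: 5.1.
- m = 12: 1.96 × √[0.16 / 720 × 4.3] = 6.1 points (4.2 to 7.4). Ignoring clustering: 2.9.

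Sessions from one participant are not independent, so treating them as such would overstate precision.

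**5. At least one session.** For example, 57 of 60 is 95%, with an exact 95% interval of 86% to 99%. This component is estimable as it stands.

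**The case against.** Group 1 is a self-described pilot and Section 9 calls the protocol exploratory, so a descriptive count is allowable and a pass mark for completion would be good practice rather than correction of an error. That stands. It does not make the count interpretable as feasibility, which is what the group is mainly for.

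Other information will exist. Section 4.2.1's at-least-one-session component, its lack-of-tolerance endpoint and the tolerability and engagement ratings in Section 3 are all usable. Section 8 has compliance reviewed after the first 10 subjects, and the table in Section 7.2 requires session-level forms at first and follow-up sessions. A reader might infer that Aim 1 as a whole cannot be assessed; these provisions show otherwise. None of them supplies sessions planned or offered. The recruitment system in Section 5.4 may hold appointments, but "Ripple is used only for storing personally identifiable information of participants and is not used to capture other research data".

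A reader might also infer that Sections 3 and 4.2.1 conflict throughout. They do not: the second half of the Section 4.2.1 endpoint, change in baseline measures, broadly matches the Aim 2 primary. Nor is the Endpoint row of the Protocol Summary, "Completion of up to twelve one-hour sessions of VR alongside study measures", clearly a third rival primary. It covers both groups and can be read as describing when participation ends.

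Finally, it is tempting to prescribe completed/planned as the sole primary. The working shows that it too moves with staff choice, so the case for it alone is not made.

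**Conclusion.** The point holds, limited to the Section 3 primary and its mismatch with the feasibility component of Section 4.2.1. Followed exactly, the plan yields a number that could be 60 or 720 in 60 participants who all tolerate VR perfectly, and a count of 240 is compatible with 33%, 50% or 100% completion. Neither the count nor the mean per participant can by itself be read as feasibility.

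The ranges rest on Group 1's 60 participants and the 1-to-12 limit, both from the protocol. The denominator example and interval widths rest on assumed values and bear on the remedy, not on whether the fault exists. This should be changed, but it does not invalidate the study.

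A separate, minor matter: Section 4.2.1 ends participation for someone "unable to complete two full VR sessions due to any possible side effect", while the closing sentence of Section 5.7 ties the two-session rule to nausea. A reader might see two contradictory stopping rules. The contrast is softer than that, because Section 5.7 opens with adverse events in general and uses nausea as its example. The two passages should still be reconciled.

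**What to change.** Before session 1, record the planned number of sessions for every Group 1 participant. For each participant, log sessions offered, sessions completed and the reason for ending: participant's decision, intolerance or staff decision.

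State one feasibility primary in the same words in the Protocol Summary and Sections 3, 4.2.1 and 9: a completion proportion, with its denominator named in advance and the group it applies to made explicit. Whichever denominator is chosen, report both completed/offered and completed/planned, with sessions not offered broken down by reason. Give a 95% confidence interval that allows for clustering within participant. Alongside it, report the proportion of enrolled participants completing at least one session, so that the Section 4.2.1 component is kept.

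Reconcile the wording of the two-session termination trigger in Sections 4.2.1 and 5.7.

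The cost is one enrolment field, a session log and wording changes. It needs no extra visits, and staff keep their discretion over the number of sessions. The downside is that completed/planned may look lower, because planned sessions that staff do not offer count as not completed; the breakdown by reason lets a reader see why. The planned number has to be captured prospectively, since it cannot be reliably reconstructed afterwards.

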4.1 Description of Study Design

Study Group 1 (Neurological Disorders):

The study is intended as a pilot trial for VR in neurological conditions. An open-label design will be implemented. Once participants are found eligible, they will complete one full session of VR using a headset preconfigured by study personnel. Participants will complete up to twelve sessions of VR therapy that may extend as long as an hour in length. Total number of study visits will be up to the study personnel's discretion. Study personnel will guide VR headset placement and program assignment (i.e., interactive or passive catalogues).

Study Group 2 (Chronic Pain in MS): The study will include an arm for people with MS (PwMS) and chronic pain. We will determine the efficacy of VR for the management of chronic pain in PwMS. Participants in this study group will receive eight treatment sessions over four weeks. Participants will be blinded to the VR treatment catalogue they receive.

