4.2.2 Study Group 2 (Chronic Pain in MS): Study Endpoints

Primary study endpoint will be change in the Patient Reported Outcomes Measurement Information System (PROMIS) pain intensity and interference measures administered at baseline, treatment end, and study end.

Secondary outcomes will include additional measures of pain and other symptoms (i.e. mood and fatigue). We will also measure the acute effects of the treatment on pain before and after each VR session.

5 Study Enrollment and Withdrawal

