Primary outcome will be the change in PROMIS Pain interference from baseline to the study end visit. Based on a previous, successful clinical trial in chronic pain also using an 8-session nonpharmacologic intervention[20], we can expect to have 89% power to detect a significant group difference between the two study conditions. We will also compare change between the groups from baseline to treatment end on the additional self-report measures.

Secondary outcomes will be change in pain visual analog scales completed before and after each session to evaluate acute treatment effects and changes in medication usage from baseline to treatment end measured qualitatively[21]. We will also analyze pain before and after each VR session with the Wong-Baker Faces Pain Rating Scale to compare the immediate analgesic effects of each condition and this cumulative change across sessions.

10 Source Documents and Access to Source Data/Documents

Data will be entered in the HIPAA-compliant NYU REDCap database designed specifically for this study. An anonymous database number will be assigned to each participant and will be used for both the Data Entry Sheet and the Patient Follow-up Sheets. The original consent, which includes the patient name and ID number, will be stored separately in a locked filing cabinet in a locked office. Access to this data will be restricted to study personnel only. Research data will be entered online through the secure NYU database software REDCap and source documents will be kept in a locked filing cabinet in a locked office. Participant data will be coded by the assigned ID and identifying information will not be presented or published to maintain participant privacy and confidentiality.

11 Quality Assurance and Quality Control

- Development of standard protocols to perform all data collection and follow-up activities.
- Use of standardized forms.
- Uniform criteria for patient recruitment.
- Standardized data processing.
- Regular communications between study staff and study investigators to resolve questions.
- Performance monitoring of data collection and data processing activities, as well as preparation of periodic reports and analyses on performance monitoring.
- Monthly monitoring of recruitment statistics.

12 Ethics/Protection of Human Subjects

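### Group 2 compares two VR conditions, so it can estimate one VR catalogue against the other but cannot determine whether VR itself works for MS pain

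*Combined protocol and SAP*

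**What the plan says.** Purpose of Group 2:

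- Section 4.1: "We will determine the efficacy of VR for the management of chronic pain in PwMS".
- Protocol Summary, Brief Summary: the MS participants with pain "will be recruited to test the analgesic effects of VR".
- Protocol Summary, Specific Aim 2: "To measure the efficacy of a VR program to manage chronic pain for people with multiple sclerosis".
- Section 5.4 says the group is recruited to look for analgesic effects.
- Section 3 gives a different second aim: "Specific Aim 2: To test the effects of immersive VR on symptom burden in patients with neurological disorders".

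Design and analysis of Group 2:

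- Protocol Summary, Methodology: "Single blinded, randomized treatment allocation to one of two VR treatment conditions". Reference Therapy is given as N/A.
- Section 4.1 blinds participants to which catalogue they receive. Section 6.1.1 describes two catalogues, one interactive and one of passively viewed 360° video, both delivered in VR.
- Section 9 makes change in PROMIS pain interference from baseline to study end the primary outcome and adds: "we can expect to have 89% power to detect a significant group difference between the two study conditions". Section 4.2.2 instead gives the primary endpoint as "change in the Patient Reported Outcomes Measurement Information System (PROMIS) pain intensity and interference measures".
- Section 9 analyses only participants who complete 6 or more of the 8 sessions. It expects 20 or more completers per group from 44 enrolled.

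**The concern.** A randomised comparison answers the question set by its arms. If both arms receive VR, whatever VR does in common to both cancels out of the difference. The trial can then say whether one catalogue does better than the other, but not whether either does better than no VR. The Section 4.1 sentence and the Brief Summary phrase promise the second answer.

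A claim about VR as such could then rest only on change from baseline. Two places leave room for that reading. The Summary's Statistical Analysis field, which covers both groups, says "Analysis will focus on change in quality of life measures from baseline to follow-up" (and also names the number of completed sessions). Section 7.1 brings Group 2 back a week after treatment to look for cumulative benefit. Section 5.2 admits people with a Brief Pain Inventory interference score of 3 or higher, and the primary outcome in Section 9 is also pain interference. Improvement within an arm would therefore mix any VR effect with regression to the mean, time and expectation.

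The 89% power adds to this: without its assumptions, a null result could be taken as a well-powered finding against VR.

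**Working it through.** **Aim against contrast.** Let I and P be the mean change under the interactive and passive catalogues, and N the mean change that the same people would have had without VR.

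- The planned contrast estimates I − P.
- The efficacy of VR would be I − N or P − N. No readable passage describes an arm that supplies N.
- I − P = 0 holds when I = P = N (neither works) and when I = P with both better than N (both work equally). The test cannot tell these apart.
- If I is better than P, the conclusion is that interactive beats passive. It bears on I against N only if passive VR is taken to be inert, and no readable passage says so.

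That the two conditions are the two catalogues is a strong inference from Sections 4.1 and 6.1.1, not an explicit statement.

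**The stated 89%.** It cannot be recomputed: the protocol gives no effect size, SD, alpha, sidedness or between-group test. Section 9 relies on a cited 8-session non-drug trial, which the reference list shows by its title to be an acupuncture trial, and on effect-size work that is not reported. What can be done is to solve for the difference that 89% implies.

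Inputs from Section 9: 44 enrolled and up to 10% dropout, so 44 × 0.90 = 39.6, or about 20 per arm. Assumed: 1:1 allocation, two-sided 5%, two-sample t-test on change, differences in units of the SD of change.

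Normal approximation: d = (1.960 + 1.227) × √(2/20) = 3.187 × 0.3162 = 1.01. The noncentral t with 38 degrees of freedom gives slightly more:

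| Analysed per arm | 80% power, two-sided | 89% power, two-sided | 89% power, one-sided 5% |
|---|---|---|---|
| 20 | 0.91 SD | 1.03 SD | 0.93 SD |
| 22 | 0.87 SD | 0.98 SD | 0.88 SD |

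95% CI half-width: 2.024 × √(2/20) = 0.64 SD at 20 per arm; 2.018 × √(2/22) = 0.61 SD at 22.

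For illustration, with values not taken from the documents: at 20 per arm, two-sided, power is 34% for a true difference of 0.5 SD and 69% for 0.8 SD.

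**The case against.** Several points on the other side have force.

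- **The schematic is missing.** The role of each arm may be labelled there. This stands: the role of passive VR is unclear in the readable text, which is not the same as absent from the plan. But the Methodology field itself calls both conditions VR.
- **Passive VR may be an attention control.** Blinding to catalogue would fit that. Even so, superiority would support the interactive catalogue over the passive one, not VR in general.
- **Not every aim statement conflicts.** Summary Aim 2 speaks of a VR program, and Section 4.1 (in its Group 1 paragraph) uses program for a catalogue, so a comparison of programs can fit. The Section 5.4 wording can also be met by a between-catalogue difference. This stands. The clear mismatch is the Section 4.1 sentence and the Brief Summary phrase.
- **Section 3 is not silent on MS.** MS is a neurological disorder, so its second aim can cover these patients. What Section 3 lacks is an aim about pain or about comparing catalogues.
- **It is a pilot.** The Summary frames the whole study as preliminary, which limits the harm. However, the explicit exploratory wording in Section 9 is attached to Group 1, while Group 2 has a power claim.

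A reader might infer that the sponsor plans to prove efficacy from pre-post change in Group 2. The documents do not support that: the paired t-tests in Section 9 belong to Group 1, and the Group 2 text there compares change between the groups. The concern is only that the broad aim leaves room for such a reading.

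**Conclusion.** The concern holds as a mismatch between claim and design. The Group 2 contrast can estimate interactive against passive VR; it cannot determine the efficacy of VR or test the analgesic effect of VR as such. This rests on the readable text and on mapping the two conditions to the two catalogues.

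The between-arm comparison starts from randomisation but is not fully protected by it. Restricting the analysis to those completing 6 of 8 sessions is a post-randomisation exclusion, and Section 5.7 ends participation after two sessions cancelled for nausea. If tolerance differs between catalogues, the analysed groups may differ too.

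The power point is secondary. It is tempting to conclude that 89% is wrong, but the documents do not show that; the inputs are missing, and the cited source cannot be checked from the protocol. Under the assumptions above, 89% corresponds to about a one-SD difference between two VR programmes (0.88 to 1.03 SD across the variants computed), which readers should be told.

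**What to change.** 1. In the Protocol Summary and Section 4.1, and as an added aim in Section 3, state the Group 2 aim along these lines: *to compare the interactive with the passive VR catalogue on change in PROMIS pain interference from baseline to study end in people with MS and chronic pain*. The sponsor should first confirm, against the schematic, that these are the two conditions and what role passive VR has. Align the Brief Summary and Section 5.4.
2. Reconcile the primary outcome between Section 4.2.2 (intensity and interference) and Section 9 (interference).
3. Add: *change from baseline within a condition will be reported descriptively and not taken as evidence that VR is efficacious*.
4. Keep the planned between-condition comparisons of pain before and after each session.
5. Optional: beside the 89%, give the implied detectable difference. Under the assumptions above: *with 20 analysed per arm, power is 80% for 0.91 SD and 89% for 1.03 SD of change; the 95% CI half-width is about 0.64 SD*.

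The cost is wording in the Summary and Sections 3, 4.1, 4.2.2, 5.4 and 9, plus sponsor decisions on the comparator role, the primary outcome and the test. No extra patients, visits or data are needed. The downside is a narrower claim: efficacy of VR against no VR is left to a later trial.
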